### 7.2.1.2.3 Grading Severity of Adverse Events

The investigator must grade the severity of all reported adverse events into one of the following five (5) categories:

- Grade 1 (Mild)
- Grade 2 (Moderate)
- Grade 3 (Severe)
- Grade 4 (Life-Threatening)
- Grade 5 (Death)

The standardized CTCAE severity grading scales for the specific type of adverse event reported must be used when a matching CTCAE term is available. The highest severity grade experienced for the event should be reported. The initial severity grading may be updated in follow-up reports if the maximum grade changes to a higher level. The CTCAE grading scale should be used according the following guidelines.

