### 7.2.1.3 Adverse Event and Serious Adverse Event Reporting

All AEs, serious and non-serious, occurring during the course of the clinical trial (i.e., from signing the informed consent through the follow-up period) will be collected, documented, and reported to the sponsor by the investigator on the appropriate eCRF and SAE reporting forms.

For each AE, the investigator will provide the onset date, end date, seriousness, grade, relatedness, treatment required, outcome, and action taken with the study agent. The investigator will determine the grade as defined in [Section 7.2.1.2.3](#) and the causal relationship to the study agent (relatedness) as defined in [Section 7.2.1.2.4](#).

The investigator must report the following events immediately (within 24 hours or the next business day whichever is shorter) to the sponsor or designee (refer to the Lab Manual/ISF for specific instructions): SAEs and non-serious AEs relevant to the reported SAE and protocol-specified AESI.

The investigator does not need to actively monitor subjects for adverse events once the clinical trial has ended. However, if the investigator becomes aware of an SAE(s) that occurred after the subject has completed the clinical trial, it should be reported by the investigator to the sponsor if considered relevant by the investigator.

Any AE occurring during the study must be documented in the subject's medical records and as an AE in the eCRF. Any SAE occurring during the study must be documented in the subject's medical records and as an SAE in the eCRF.

A separate SAE report should be used for each SAE. However, if at the time of initial reporting, multiple SAEs are present that are temporally and/or clinically related, they may be reported on the same SAE report.

The investigator should attempt to establish a diagnosis of the event (that meets the definition of an AE or SAE) based on signs, symptoms, and/or other clinical information. In such cases, the diagnosis should be

documented as the AE and/or SAE and not the individual signs or symptoms. The diagnosis will become the basis for the verbatim term as reported by the investigator. If no diagnosis is known and clinical signs and symptoms are not present, the abnormal finding should be recorded.

The investigator will take all appropriate and necessary therapeutic measures required for resolution of the AE. Any medication necessary for the treatment of an AE must be recorded on the concomitant medication case report form.

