## 8.2.1 SCREENING AND RUN-IN PERIOD

The screening period (Visit 1), i.e. the phase after informed consent and before the first administration of the study agent, may be as long as 6 days (day -7 to -2). However, a pretrial fundus photography/FA examination performed within 14 days prior to Visit 1 can be used as the screening ophthalmologic examination. In special cases where it is not logistically possible to meet the protocol defined screening period, the screening can be extended by an additional 7 days (day -14) without repeating the screening assessment.

The medical history and medication history within 3 months prior to Visit 1, as well as baseline condition of the subject, will be captured in the eCRF.

### 8.2.1.1 Visit 1

At Visit 1, the following procedures and assessments are performed:

- Signing of all applicable Informed Consents
- Potential study subject eligibility based on all study-specific inclusion and exclusion criteria (see [Sections 5.1](#) and [5.2](#))
- Demographics and medical history
- All ophthalmological evaluations: BCVA, SD-OCT, fundus photography/FA, slit lamp, and IOP (see [Sections 7.1](#) and [7.2.5](#))
- Vital signs, physical examination, safety laboratory tests, **Poland only**: serum pregnancy test (in women of childbearing potential), and 12-lead ECG, (see [Sections 7.2.2](#), [7.2.3](#) and [7.2.4](#))
- Review of concomitant medications (see [Sections 6.3](#) and [6.4](#))
- AE reporting and evaluation according to [Section 7.2.1](#)

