16.1 Adverse Events

AEs are defined as any untoward medical occurrence associated with the use of an IMP in humans, whether or not considered IMP-related. All AEs, serious and non-serious, occurring during the course of the clinical trial (i.e., from signing the informed consent through the follow-up period) will be collected, documented, and reported. All AEs that occur or worsen on or after the first use of IMP will be considered as treatment-emergent AEs (TEAE). Reported AEs that begin prior to the first dose of IMP are classified as non-TEAEs; these will only be included in subject listings and not included in summary tables.

When reporting an AE, the event description should use the best matching terminology describing the event as found in the Common Terminology Criteria for Adverse Events (CTCAE v4.03). Standardized terms from the CTCAE will be used to categorize events for reporting to regulatory authorities using the Medical Dictionary for Regulatory Activities (MedDRA, v. 21.0).

The severity of all reported AEs are graded by the investigator into one of the following five (5) CTCAE categories:

- Grade 1 (Mild)
- Grade 2 (Moderate)
- Grade 3 (Severe)
- Grade 4 (Life-Threatening)
- Grade 5 (Death)

The relatedness of IMP to AE will be classified as definite, possibly, or unrelated. Documentation of AEs will include start date, end date, seriousness, severity, relatedness, whether or not medication was required, outcome, and action taken with the study agent.

A serious adverse event (SAE) is defined for this protocol as any AE that meets one or more of the following criteria:

- A death (CTCAE Grade 5 event) occurring during the study, whether or not considered treatment-related;
- A life-threatening event (CTCAE Grade 4);

- An event requiring inpatient hospitalization or prolonged hospitalization due to the adverse event;
- An adverse event resulting in a significant, persistent, or permanent change, impairment, damage or disruption in the participant's body function or structure, physical activities or quality of life;
- An event that otherwise required a medical or surgical intervention to preclude permanent impairment or damage (excluding unrelated elective or cosmetic procedures).

An AE of special interest (AESI) is defined for this protocol as any the following outcomes:

- Hepatic injury defined by the following alterations of liver parameters:

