 - For subjects with normal liver function at baseline an elevation of aspartate aminotransferase (AST) and/or alanine aminotransferase (ALT) ≥ 3 -fold the upper limit of normal (ULN) combined with an elevation of total bilirubin ≥ 2 -fold the ULN measured in the same blood draw sample;
- Abrupt decrease of BCVA (> 15 letters lost from baseline);
- QTc interval prolongation ($> +50$ ms from baseline and > 450 ms).

An overall tabular summary of TEAEs will be presented that includes the number and percentage of subjects who experienced at least one TEAE. These summaries will also include breakdowns of TEAEs further categorized as ocular or non-ocular, and within these categories as drug-related TEAEs, TEAEs with CTCAE Grade 3/4/5, drug-related TEAEs with CTCAE Grade 3/4/5, TEAEs with an outcome of death, serious TEAEs, drug-related serious TEAEs, TEAEs leading to discontinuation of IMP and drug-related TEAEs leading to discontinuation of IMP.

Furthermore, the number and percentage of subjects with TEAEs by SOC and PT; by SOC, PT and maximal severity; by SOC and PT for TEAEs; by SOC and PT for SAEs; and by SOC and PT for TEAEs leading to subject withdrawal will be presented. Separate summaries will be provided for ocular and non-ocular TEAEs (including systemic). Adverse events of special interest will also be summarized by SOC and PT. These summaries by SOC and PT will be at the subject level. If a subject reports the same PT multiple times within the same SOC, that PT will only be counted once within that SOC. As with the PT, if a subject reports multiple conditions within the same SOC, that SOC will only be counted once.

All AEs (including non-TEAEs) will also be presented in subject listings.

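### SAP 16.1 gives conflicting rules for adverse events that start between consent and first dose and then worsen on drug; one rule keeps them out of the AE summary tables

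*SAP*

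**What the plan says.** SAP 16.1 (Adverse Events) sets out two rules in consecutive sentences.

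- Rule A: "All AEs that occur or worsen on or after the first use of IMP will be considered as treatment-emergent AEs (TEAE".
- Rule B: "Reported AEs that begin prior to the first dose of IMP are classified as non-TEAEs; these will only be included in subject listings". The rest of that sentence makes the exclusion explicit: "and not included in summary tables".

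Later in the same section the SAP confirms that nothing is lost from the listings: "All AEs (including non-TEAEs) will also be presented in subject listings".

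AEs are collected "from signing the informed consent through the follow-up period" (Protocol 7.2.1.3), so events with a pre-dose start are part of the data. Protocol 8.2.1 says the screening period "may be as long as 6 days (day -7 to -2"), and that in special cases "the screening can be extended by an additional 7 days (day -14) without repeating the screening assessment".

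On worsening of an AE already on record, Protocol 7.2.1.2.3 says: "The initial severity grading may be updated in follow-up reports if the maximum grade changes to a higher level".

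**The concern.** For one kind of event the two rules give opposite answers: an AE that begins after consent and before first dose, then worsens on drug. The SAP states no order of precedence, the protocol does not define a TEAE, and SAP section 21 records no change from the protocol that would settle the matter.

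The AE profile is the trial's only secondary endpoint. The overall, related, serious, withdrawal and maximum-severity AE tables in SAP section 24 are all built on TEAEs. Rule B can only take events out of those tables. The events it takes out are those in which a drug effect would show as aggravation of something already present. A Grade 1 event at screening that became Grade 3 or serious on drug would be missing from all of these tables.

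The single interim analysis (SAP section 18) also rests on AE data and can stop recruitment, so the same event should not be classified differently there and at the final analysis.

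**Working it through.** The plan gives no figure to reproduce. The check applies both rules to each possible AE timing, asks which rule the data items support, and then bounds the size.

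**Step 1. Apply both rules.**

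| Timing of the event | Rule A | Rule B | Result |
|---|---|---|---|
| Starts on or after first dose | TEAE | silent | agree |
| Starts between consent and first dose, does not worsen | not a TEAE | non-TEAE | agree |
| Starts between consent and first dose, worsens on or after first dose | TEAE | non-TEAE | **conflict** |
| Condition present before consent, worsens on drug | TEAE (Protocol 7.2.1.2.5 records the worsening as an AE, normally with an on-treatment start) | silent | agree |

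Only the third row conflicts.

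**Step 2. See which rule the data items support.**

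- Protocol 7.2.1.2.3 asks for the highest grade and allows the grade of the existing event to be raised. It does not call for a new record or a new start date.
- The AE items listed in Protocol 7.2.1.3 and SAP 16.1 include a start and an end date. They include neither a date of worsening nor a grade at first dose.
- SAP 9.1 uses imputed dates to derive treatment emergence, so the derivation is at least partly date-driven.

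Rule B needs only the start date. Rule A, for the third row, needs information that is not on the list. That makes rule B the likelier one in programming, although the documents do not say so.

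**Step 3. Length of the window.** Pre-dose days are Day -7 to Day -1 (7 days), or Day -14 to Day -1 (14 days) if screening is extended. Collection runs to the Day 71 call.

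- Standard: 7 / (7 + 71) = 7/78, about 9% of the collection period.
- Extended: 14 / (14 + 71) = 14/85, about 16%.

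These are shares of time, not of events. Only AEs that start in that window and then worsen on drug are in conflict.

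**Step 4. Size.** Take 30 treated subjects (the planned enrolment). Let k be the number with an event in the third row, and m ≤ k the number of those with no other TEAE. Understatement of overall TEAE incidence = 100 × m / 30 points.

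| k (assumed) | m = 0 | m = k |
|---|---|---|
| 1 | 0 | 1/30 = 3.3 points |
| 2 | 0 | 2/30 = 6.7 points |
| 3 | 0 | 3/30 = 10 points |

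The documents give no AE rate, so k cannot be derived from them. The same 3.3 points per subject applies to a single row of a preferred-term, serious or severity table when the subject has no other TEAE that counts in that row.

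**The case against.** The strongest reply is that rule B is meant as the complement of rule A: it describes pre-dose AEs that do not qualify as TEAEs, and a reader who starts with rule A would keep a worsened event in the tables. That reading is possible, and for that reason the outcome is unresolved rather than a settled exclusion. It does not remove the conflict, because rule B is written without any exception.

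A reader might go further and infer that all on-treatment worsening disappears from all safety tables. The documents do not support this, for three reasons.

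- Worsening of the disease under study or of other earlier conditions is recorded as an AE in its own right (Protocol 7.2.1.2.5). ECG abnormalities at screening are entered as baseline conditions (Protocol 7.2.3). Two of the three AEs of special interest, loss of visual acuity and QTc prolongation, are defined by change from baseline and should not have a pre-dose start.
- The laboratory, ECG, vital-sign, IOP and slit-lamp summaries (SAP 16.2 to 16.6) do not depend on TEAE status.
- Every AE is listed, and the listings for about 30 open-label subjects can be read in full.

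A reader might also infer that such events are bound to occur because screening can reach back to Day -14. That extension is for special cases only. Collecting AEs from consent shows that pre-dose AEs are possible, not that any will worsen on drug.

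Finally, 1 to 3 affected subjects might be read as a loss of 3 to 10 points. That holds only if none of them has another TEAE. Without that condition the lower end is 0.

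All of these limits stand. They narrow the point but leave the contradiction in place for the third row of the table.

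**Conclusion.** The point holds in a narrow form. SAP 16.1 contradicts itself on AEs that begin between consent and first dose and worsen on drug. If rule B is applied, those events appear in listings only, and the TEAE counts (overall, serious and by severity) fall or stay the same; they cannot rise.

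The size is 3.3 points of overall TEAE incidence per affected subject with no other TEAE, or 0 to 10 points if 1 to 3 of 30 subjects are affected. Both the number affected and the denominator of 30 treated subjects are assumptions. The effect may well be nil. The reason to act is that any error runs in the favourable direction on the only secondary endpoint, in a trial with no control arm, and that the correction is cheap.

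**What to change.** Make three changes in SAP 16.1, before database lock and with the same rule used at the interim analysis.

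1. Replace rule B with: *AEs that begin before the first dose and do not increase in CTCAE grade or become serious on or after the first dose are non-TEAEs.* This makes it the true complement of rule A.
2. State that a worsened event counts as a TEAE at its on-treatment maximum grade.
3. State how worsening is identified: either a new AE record opened when the event worsens, or the grade at first dose together with the date of the increase. Without this the first two changes cannot be programmed, because the listed AE items hold neither.

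The cost is a sentence or two of SAP text, a small data-recording convention for the sites and data management, and a grade-change check in programming. Reported AE rates may come out slightly less favourable.

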16.2 Slit-Lamp Biomicroscopy Examination

Slit-lamp biomicroscopy examinations will be conducted on both eyes at all scheduled visits. The slit-lamp findings will include examinations of the cornea, conjunctiva, anterior chamber, iris/pupil, lens and

eyelids. Anterior chamber will be graded as +, ++, +++ or none; the other parameters will be graded as normal or abnormal. Abnormal findings will be further classified as not clinically significant (NCS) or clinically significant (CS). All clinically significant values will be recorded as AEs in the eCRF and followed until resolution. Once resolved, the AE eCRF page(s) will be updated

Slit-lamp findings will be summarized by visit, for the study eye and fellow eye separately, using qualitative summary statistics (frequency counts and percentages). Percentages will be based on the number of subjects with non-missing values at a given visit.

A shift table will show changes from baseline Visit 2 (Day 1) to all observations at later study visits. The data for slit-lamp biomicroscopy examinations will be presented in a listing.

16.3 Intraocular Pressure (IOP)

IOP will be measured using applanation Goldmann tonometry or equivalent tonometer in both eyes at all scheduled visits. IOP will be summarized for each eye (study eye and fellow eye) by visit using quantitative summary statistics. The number and percentage of subjects with IOP \geq 20 mmHg and the number and percentage of subjects with IOP \geq 30 mmHg will be summarized. Results will be listed for both eyes at each visit.

16.4 Clinical Laboratory Values

Blood samples and urine must be collected at every visit. Safety laboratory examinations will include hematology, biochemistry, coagulation, and qualitative urine analysis.

- Serology (screening only): hepatitis A (anti-immunoglobulin M (IgM), anti-IGM)), hepatitis B (hepatitis B antigen, anti-HBs, DNA), hepatitis C (anti-hepatitis C virus (HCV), ribonucleic acid (RNA) if anti-HCV positive), hepatitis D (anti-IgM, anti-immunoglobulin G (IgG)), hepatitis E (anti-hepatitis E virus (HEV), anti-HEV IgM, RNA if anti-HEV IgM positive), anti-smooth muscle antibody (titer), anti-nuclear antibody (titer), anti-liver-kidney microsomes (LKM) antibody, antimitochondrial antibody, Epstein Barr virus (vascularized composite allotransplantation (VCA) IgG, VCA IgM), cytomegalovirus (IgG, IgM), herpes simplex virus (IgG, IgM), varicella (IgG, IgM), parvovirus (IgG, IgM), toxoplasmosis (IgG, IgM)
- Hematology: hemoglobin, red blood cell count (RBC), white blood cell count (WBC) with differential, platelets
- Biochemistry: glucose, sodium, potassium, calcium, inorganic phosphate, creatinine, aspartate aminotransferase (AST), alanine aminotransferase (ALT), alkaline phosphatase (AP), lactate dehydrogenase (LDH), total bilirubin (if elevated provide direct bilirubin), urea, total protein, albumin, uric acid

- Coagulation: activated partial thromboplastic time (aPTT), prothrombin time (PT)/international normalized ratio (INR)
- Urine: potential of hydrogen (pH), glucose, erythrocytes, leukocytes, protein, nitrite and glomerular filtration rate (GFR)

All safety laboratory measurements will be performed at all scheduled visits by a central laboratory (except serology which is evaluated at screening only) . Investigators will get guidance and instructions on laboratory sampling and processing through a separate Lab Manual provided by the central laboratory.

The investigator is responsible for determining and documenting if out of range laboratory values are clinically significant or not. All clinically significant values will be recorded as AEs in the eCRF and followed until resolution. Once resolved, the AE eCRF page(s) will be updated.

Continuous biochemistry, hematology, and coagulation assessments will be summarized by visit and changes from baseline using quantitative summary statistics. The data for biochemistry and hematology will also be presented in listings.

Serology and urinalysis will be listed with collection information, and clinically significant findings, but no tabular summaries will be produced.

All laboratory values will be presented using conventional units.

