### 2.3.1 KNOWN POTENTIAL RISKS

ALK4290 was considered safe and well tolerated by the subjects with wAMD in the trial. Potential risks associated with the study design include those related to the study procedures and methodology, most notably the potential risks associated with FA including allergic reactions and renal/ thyroid complications.

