**7.2.2 SAFETY LABORATORY EVALUATIONS**

Blood samples and urine must be collected at every visit. Safety laboratory examinations will include hematology, biochemistry, coagulation and qualitative urine analysis.

- Hematology: hemoglobin, red blood cell count (RBC), white blood cell count (WBC) with differential, platelets
- Biochemistry: glucose, sodium, potassium, calcium, inorganic phosphate, creatinine, aspartate aminotransferase (AST), alanine aminotransferase (ALT), alkaline phosphatase (AP), lactate dehydrogenase (LDH), total bilirubin (if elevated provide direct bilirubin), urea, total protein, albumin, uric acid
- Coagulation: activated partial thromboplastin time (aPTT), prothrombin time (PT)/international normalized ratio (INR)
- Urine: potential of hydrogen (pH), glucose, erythrocytes, leukocytes, protein, nitrite

Glomerular filtration rate (GFR) will be estimated by the Cockcroft Gault Formula utilizing serum creatinine (see [Section 17.5](#)). All safety laboratory measurements will be performed by a central laboratory. Investigators will get guidance and instructions on laboratory sampling and processing through a separate Lab Manual provided by the central laboratory.

The investigator is responsible for determining and documenting if out of range laboratory values are clinically significant or not. All clinically significant values will be recorded as AEs in the eCRF and followed until resolution. Once resolved, the appropriate eCRF page(s) will be updated.

---

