**17.5 COCKCROFT-GAULT FORMULA**

Glomerular filtration rate (GFR) may be estimated based on the commonly used and accepted formula, the Cockcroft-Gault formula:

$$GFR = \frac{(140 - \text{age}) \times \text{weight} \times F_s}{\text{Serum Creatinine} \times 72}$$

Units: GFR [ml/min], age [years], weight [kg], serum creatinine [mg/dl], FS is a correction Factor for Sex: in males FS = 1, in females FS = 0.85

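### SAP 16.4 lists GFR as a urine test, so a value calculated from serum creatinine gets a listing but no by-visit, change-from-baseline or shift table (minor)

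*SAP*

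**What the plan says.** Protocol 7.2.2 gives the urine panel as "Urine: potential of hydrogen (pH), glucose, erythrocytes, leukocytes, protein, nitrite", with no GFR. It then says separately: "Glomerular filtration rate (GFR) will be estimated by the Cockcroft Gault Formula utilizing serum creatinine". Protocol 17.5 sets out the formula and its inputs: "Units: GFR [ml/min], age [years], weight [kg], serum creatinine [mg/dl], FS is a correction Factor for Sex". None of these inputs comes from urine.

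SAP 16.4 gives the urine panel as "Urine: potential of hydrogen (pH), glucose, erythrocytes, leukocytes, protein, nitrite and glomerular filtration rate (GFR"). Its reporting rules then differ by panel:

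- "Continuous biochemistry, hematology, and coagulation assessments will be summarized by visit and changes from baseline using quantitative summary statistics".
- "Serology and urinalysis will be listed with collection information, and clinically significant findings, but no tabular summaries will be produced".

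The SAP table index agrees. Tables 14.3.10.1.1 to 14.3.10.3.2 are summary and shift tables for biochemistry, coagulation and hematology. Urine has only Listing 16.2.8.8. No table, listing or figure title mentions GFR.

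Protocol 10.4.2 and SAP 16 both name change from baseline in laboratory values as a safety endpoint. SAP 21 declares no changes from the protocol's analyses.

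**The concern.** GFR is a continuous quantity derived from blood, but the SAP files it in a panel that it calls qualitative and does not tabulate. A programmer who follows the text will produce no GFR table. GFR is also the measure by which the protocol defines impaired renal function at entry (below 30 mL/min is excluded, Protocol 5.2). A reader of the study report would expect to see how it is distributed on treatment and whether anyone fell below that value. Protocol 2.3.1 also names renal complications as a potential risk, in connection with fluorescein angiography (FA): "most notably the potential risks associated with FA including allergic reactions and renal/ thyroid complications".

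**Working it through.** The documents give no figure to reproduce. The check has three steps: trace the rule, see what the creatinine tables can replace, and see which visits bear on the named risk.

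**1. Tracing the rule.** The SAP files GFR under urine. Urinalysis is listed only. The index has no other GFR output. So GFR has no by-visit, change-from-baseline or shift summary. Creatinine and urea are on the SAP's biochemistry line, so they have all three.

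**2. What the creatinine tables can replace.** Protocol 17.5 gives

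GFR = (140 − age) × weight × FS / (72 × creatinine), with FS = 1 for men and 0.85 for women.

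*Change within a subject.* Over six weeks age and sex are fixed and weight nearly so. Then GFR after / GFR before = creatinine before / creatinine after. Take an assumed woman aged 75, 65 kg, whose creatinine rises from 0.8 to 1.1 mg/dL:

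- Before: 65 × 65 × 0.85 / (72 × 0.8) = 3591.25 / 57.6 = 62.3 mL/min.
- After: 3591.25 / (72 × 1.1) = 3591.25 / 79.2 = 45.3 mL/min.
- Ratio: 45.3 / 62.3 = 0.727, a fall of 27%. This equals 0.8 / 1.1 = 0.727.

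The matching creatinine change is +0.3 mg/dL, or 0.3 / 0.8 = +37.5%. It enters the planned change-from-baseline table, which under SAP 9.4 includes the minimum and maximum. The range-based shift table shows it only if 1.1 mg/dL is above the laboratory's upper limit. The documents give no reference range, so either outcome is possible.

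*Absolute level across subjects.* Four assumed patients, all with creatinine 1.2 mg/dL (72 × 1.2 = 86.4):

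| Assumed patient | Numerator | GFR (mL/min) |
|---|---|---|
| Man, 55 years, 90 kg | 85 × 90 × 1 = 7650 | 88.5 |
| Man, 75 years, 70 kg | 65 × 70 × 1 = 4550 | 52.7 |
| Woman, 75 years, 70 kg | 65 × 70 × 0.85 = 3867.5 | 44.8 |
| Woman, 85 years, 50 kg | 55 × 50 × 0.85 = 2337.5 | 27.1 |

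The same creatinine spans about 27 to 89 mL/min and both sides of 30. The creatinine tables therefore show change well enough, but cannot give the GFR distribution or a count below a threshold.

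**3. Which visits bear on the FA risk.** The schedules of events place FA at screening and at Visit 8. The first FA precedes the Visit 2 baseline, so any effect still present by then is already in the baseline. The laboratory visits after the second FA are Visits 9 and 10.

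**A gap in the derivation.** Laboratory tests are done at Visits 1 to 10. Weight is taken with the physical examination, at Visits 1, 2, 4, 6, 8 and 10 (SAP 16.7). Visits 3, 5, 7 and 9 therefore have creatinine without a same-day weight, and Visit 9 is the first visit after the second FA. Neither document says which weight to use.

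**The case against.** The strongest reply is that little is lost. Creatinine and urea are summarized by visit, as change from baseline and as shifts, and within a subject the GFR change is almost exactly the inverse of the creatinine change. Individual GFR values would still be listed, and with about 30 subjects a listing can be read line by line. The investigator assesses out-of-range values, and those judged clinically significant become adverse events, which are tabulated. The 30 mL/min limit is an entry criterion and does not by itself call for longitudinal tables. All of this stands, and it is why the point is minor. It does not make GFR a urine test or supply the threshold counts.

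A reader might infer that renal safety goes unreported, or that a renal risk of ALK4290 would be hidden. The documents support neither. Renal markers are tabulated, and Protocol 2.3.1 attaches the named renal risk to FA, not to the study agent. Nor do they show a deliberate change of analysis. In Protocol 7.2.2 the GFR sentence directly follows the urine bullet, and SAP 21 declares no changes, so a drafting slip is the likelier explanation.

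It can also be objected that using an earlier weight conflicts with SAP 9.1, which allows no imputation except for dates, and that later weights may not be available, since SAP 16.7 lists only whether the examination was done. Both objections are fair, and the fix has to deal with them.

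**Conclusion.** The misclassification is certain from the text, and so is its effect on the planned tables. The effect on conclusions is small. What is missing is the distribution of absolute GFR and the number of subjects crossing a threshold such as 30 mL/min. Change in renal function is largely visible through creatinine, and no efficacy result is touched. The patient examples are assumed and show only that creatinine cannot stand in for absolute GFR. They do not predict what the trial will find. The inverse relation between the two changes assumes nearly constant weight over six weeks. Severity: minor.

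**What to change.** - **SAP 16.4:** remove GFR from the urine line and enter it under biochemistry as a derived parameter, calculated by the formula in Protocol 17.5.
- **Tables 14.3.10.1.1 and 14.3.10.1.2:** add GFR as value by visit, change from baseline, and shift across prespecified categories that include the protocol's 30 mL/min. The sponsor should fix any other cut-points before the analysis. Visits 9 and 10 should be shown, as the laboratory visits after the second FA.
- **Weight rule:** state that the most recent recorded weight is used, or the baseline weight if later weights are not in the database. SAP 11.1 already lists weight among the demographic variables. GFR is proportional to weight, so a 1% error in weight is a 1% error in GFR.
- **SAP 9.1:** note that this is a derivation rule for a laboratory parameter and not imputation of an endpoint.

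The cost is a few lines of SAP text, one derived parameter and extra rows in two planned tables. It needs no new samples or visits. Someone must check whether post-baseline weights are in the database.
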